# 10 Statistical Considerations

## 10.1 Primary endpoints

### 10.1.1 Efficacy

1. Change in  $\text{PaO}_2/\text{FiO}_2$  ratio from baseline (as defined in sections 7.1.2 and 7.1.3), daily during treatment, end of treatment, 3 days post end of treatment and 5 days post end of treatment.

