## 10.5 Randomisation methods

No randomisation will be employed in this pilot study due to practical and ethical considerations.

A statistically powered RCT would be ideal to define the magnitude of benefit and impact on overall survival and is the typical design in patients with ARDS. Although there is clinical data on the safety of nebulised rtPA, but there are no clinical data on this condition to facilitate a sample size calculation. There are data from a small RCT that has used another fibrinolytic agent, but the doses are not comparable (Abdelaal Ahmed Mahmoud et al. 2020). If a patient is randomised to receive no treatment, this precludes participation in other interventional studies which might increase the risk of mortality. The most recent figures suggest a 50% mortality in patients receiving

IMV. (<https://www.icnarc.org/About/Latest-News/2020/04/04/Report-On-2249-Patients-Critically-III-With-Covid-19>) Currently there is a concerted effort to introduce multiple therapies based on our understanding of the pathophysiologic basis of disorder. Ethical concerns were raised about the potential for denying patients new treatment strategies when randomised to standard of care arm. The management strategies are evolving on an unprecedented scale with repurposing of existing medications, many of which are proof of concept of studies. Further, if this pilot study shows significant effect in a subset of patients, there would be justification to progress to a statistically powered RCT. We would progress to a RCT only after submission of a substantial amendment to this trial protocol or submission of a new clinical trial application. In the event of major adverse drug reactions or minor improvement in the oxygenation as assessed by  $\text{PaO}_2/\text{FiO}_2$ , there are minimal gains to be had with a larger randomised control study.

A Data Monitoring Committee (DMC) will be set-up to review safety data within the trial along with the final study results and advise on progressing from a pilot study to a statistically powered RCT based on the safety and efficacy data that is collected.

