6.1 General statistical considerations

All analyses will be descriptive in nature and should be considered as hypothesis generating rather than providing firm conclusions. All statistical tests and confidence intervals will be 2-sided. Significance will be considered at the 5% level and confidence intervals will be at the 95% level.

Analyses for both primary and secondary outcomes will be conducted following an Intention To Treat (ITT) approach, and non-compliance will be reported at the individual patient level. No adjustments for missing data will be made.

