6.3 Analysis of primary outcome

The primary outcome for efficacy is oxygenation, measured using the PaO₂/FiO₂ ratio over time. The distributions of the primary outcomes will be summarised, by group, over time. Change in PaO₂/FiO₂ ratio from baseline will be checked visually using means & SE plots. If necessary, appropriate transformations of the data will be performed (e.g., using the natural logarithm).

Subject to the final sample size and data quality, PaO₂/FiO₂ ratio will also be compared between the SOC group (historical controls) and rtPA group using appropriate regression modelling, controlling for baseline oxygenation ratio:

$$OXY_i = \beta_0 + \beta_1 \cdot T_i + \beta_2 \cdot OXY0_i + \varepsilon_i,$$

where the i subscript denotes the i^{th} patient and

- OXY_i = PaO₂/FiO₂ ratio (oxygenation) at the end of treatment;
- T_i = group indicator (= 1 if patient is in the rtPA group, = 0 otherwise);
- $OXY0_i$ = PaO₂/FiO₂ ratio (oxygenation) at baseline;
- $\varepsilon_i \sim N(0, \sigma^2)$ = Normally distributed error term.

The estimate of the parameter β_1 and associated 95% confidence interval shall be reported, as well as a p-value pertaining to the hypothesis test of

$$H_0: \beta_1 = 0 \text{ versus } H_1: \beta_1 \neq 0.$$

Similarly, the use of models using oxygenation at other meaningful timepoints as outcome measure will be evaluated. Owing to a limited sample size, models shall not adjust for other baseline characteristics. Fitted models shall be checked, where appropriate, to ensure that modelling assumptions have been satisfied. Appropriate transformations of outcomes or other suitable approaches (e.g., robust or non-parametric methods) shall be explored if model assumptions are not satisfied.

For treatment safety, the incidence and severity (either major or minor) of bleeding events will be summarised with frequencies and percentages in each group. Fibrinogen levels will also be summarised graphically using plots of the mean, by group, over time. Finally, the number and nature of serious adverse events (SAEs) will be summarised. These events are defined in section 8 of the protocol.

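### The SAP's P/F comparison rests on an end-of-treatment day with no counterpart in controls and leaves further timepoints open at 5%, while the protocol ties RCT progression to a significant effect

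*SAP*

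**What the plan says.** Protocol 10.1.1 defines the primary efficacy endpoint as change in P/F from baseline, "daily during treatment, end of treatment, 3 days post end of treatment and 5 days post end of treatment". SAP 6.3 summarises P/F by group over time, with plots of means and standard errors. Subject to sample size and data quality, it then regresses P/F ("oxygenation) at the end of treatment") on group and baseline P/F. It reports the group coefficient with a 95% CI, "as well as a p-value pertaining to the hypothesis test of" no group difference. It adds that "the use of models using oxygenation at other meaningful timepoints as outcome measure will be evaluated".

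SAP 6.1 states: "All statistical tests and confidence intervals will be 2-sided". It continues: "Significance will be considered at the 5% level and confidence intervals will be at the 95% level". The same paragraph says: "All analyses will be descriptive in nature and should be considered as hypothesis generating rather than providing firm conclusions". Neither document gives a multiplicity rule.

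Protocol 4.1 and 10.5 both say that "if this pilot study shows significant effect in a subset of patients", moving to a powered RCT would be justified.

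**The concern.** There are three linked difficulties.

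- **The one written outcome is not anchored.** End of treatment falls on different days in different treated patients and may be brought about by improvement itself. Controls receive no rtPA, so they have no such day, and the SAP does not assign one.
- **The list of further models is open.** Neither the number nor the identity of the other timepoints is fixed, and the 5% level applies to every test.
- **The descriptive label sits beside a decision.** The plan disclaims firm conclusions, yet it sets a significance level, asks for a p-value, and uses the language of significance for progression to an RCT.

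With 9 treated patients and 18 controls (protocol 4.1), the progression decision could rest on whichever timepoint happened to cross 5%.

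**Working it through.** **1. Is end of treatment a common day?**
- Protocol 7.3 and 7.3.1 give a minimum of 5 days initially and a maximum of 14.
- Protocol 7.3.3 allows earlier stopping, including after 48 hours of saturation on room air that is normal for the patient. The day can therefore depend on response.
- For controls, protocol 7.5.2 collects data where available for 28 days from hospital admission. The SAP appendix mentions day 7 for SOC patients as a limit for four-hourly extraction, not as an analysis day.
- SAP 6.2 and protocol 10.6.1 take the control baseline as the last value before enrolment and refer to a section 8.2 for the definition. In the current protocol, section 8.2 covers recording of adverse events. Day 1 for controls is therefore unclear as well.

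**2. How many timepoints could qualify?** With 14 treatment days, the endpoint offers 14 daily values (the last being end of treatment) plus two post-treatment values, so 14 + 2 = 16.

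**3. Error rate with no true effect.** The plan states no power, effect size or SD, so it has no figure to reproduce beyond the 5% per test. Within-patient correlation is not given either and is assumed. The SAP's regression was simulated for 9 v 18.

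| Tests run, any p<0.05 acted on | Independent: 1 − 0.95^k | Simulated, correlated |
|---|---|---|
| End-of-treatment test only | 5% | about 5% |
| 3 (end of treatment, +3, +5 days) | 14.3% | 11-14% |
| 5 (days 5, 7, 14, 17, 19) | 22.6% | 16-21% |
| 16 (all) | 56.0% | 33-46% |

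The five-timepoint row assumes AR(1) correlation of 0.7-0.95 per day. The three- and sixteen-timepoint rows assume constant correlation of 0.5-0.9 or AR(1) of 0.8-0.9. Correlation holds the rate below the independent figure, so the error does not rise in proportion to the number of tests. The five days are an illustration and are not taken from the SAP.

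**4. Precision of one day against a seven-day mean.** Assume constant correlation r between any two days and take the variance after baseline adjustment, in units of the between-patient variance:
- single day: 1 − r²
- mean of seven days: (1 + 6r)/7 − r²

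| r | Single day | Seven-day mean | SD ratio |
|---|---|---|---|
| 0.3 | 0.91 | 0.31 | 0.58 |
| 0.5 | 0.75 | 0.32 | 0.65 |
| 0.7 | 0.51 | 0.25 | 0.70 |

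The residual SD is 42%, 35% and 30% lower respectively. For scale, the single-timepoint 95% CI half-width with 9 v 18 is about 2.06 × √(1/9 + 1/18) = 0.84 residual SD.

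**5. When averaging does not help.** If the effect builds linearly to its full size on day 7, the mean over days 1-7 captures (1+2+…+7)/(7×7) = 4/7 of it. Dividing 4/7 by the SD ratios gives signal-to-noise relative to day 7 of 0.98, 0.87 and 0.81. If the effect builds to day 14, the mean captures 4/14, and the figures relative to day 14 are 0.49, 0.44 and 0.41.

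**The case against.** The strongest defence is that this is an openly exploratory pilot. One model is written out in advance, and that test keeps its 5% level. The SAP says the use of other models will be evaluated, which is not a promise to test them, and the whole comparison is conditional. Progression also depends on DMC advice on safety and efficacy together, and on a substantial amendment or new application (protocol 10.5 and 12.2). The word significant there is set against minor improvement and may mean size of effect. A false lead would bring a powered trial, not an efficacy claim. All of this stands. It limits the consequence but does not supply the missing control day, close the list of timepoints, or settle what significant means.

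A reader might infer three stronger points that the documents do not support.
- **That daily data are discarded.** They are summarised and plotted by group (SAP 6.3, protocol 10.6.2); only the regression uses one value.
- **That false positives reach 35-45%.** Simulation gives about that if regressions within the IMV and non-invasive groups are added at the five illustrative days. The SAP writes no subgroup regression, and protocol 10.6 treats ventilation type by summaries.
- **That a first-week mean is simply better.** Step 5 shows it loses when the effect builds over time. It is partly a change of estimand.

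**Conclusion.** The concern holds in a limited form. The between-group outcome is tied to a day that varies among treated patients and is undefined for controls. The further timepoints are open, and the progression wording can be read as resting on any one of them. No confirmatory error rate is breached, because none is claimed.

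The 16-21% chance of a false lead requires that all five example models are run and any p<0.05 is acted on, under the assumed AR(1) correlation. It would be higher if subsets were also tested, which the SAP does not plan. The 30-42% reduction in residual SD rests on assumed constant correlation of 0.3-0.7, and it is a net gain only if the effect is roughly constant over the averaged days. The point concerns cohort 1; protocol 10.6 provides a separate SAP for cohort 2. The plan should be changed, since the change is mainly one of wording.

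**What to change.** - **SAP 6.3:** name one between-group contrast on fixed study days applied to both groups. Define day 1 for controls and state how death and discharge enter the outcome. The baseline-adjusted mean of daily P/F over days 1-7 is one suitable choice. Report the estimate and 95% CI and drop the p-value.
- **Data coverage:** control data to day 7 are not assured, since they are collected only where available. SAP 6.1 makes no adjustment for missing data. Report the number of days contributing per patient, by group.
- **Other timepoints:** show end of treatment and all other days as estimates with CIs, without significance claims.
- **SAP 6.1:** remove the 5% significance level, which then agrees with the descriptive label.
- **Protocol 4.1 and 10.5:** replace the reference to a significant effect in a subset with this estimate and its interval, overall and descriptively by ventilation type.

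The cost is wording in the SAP and two protocol sections, with no new patients or data. If the first-week mean is chosen, the main estimate becomes a first-week average that would dilute a late effect. The end-of-treatment values remain in the tables.

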#### **10.4.2 Historical control recruitment – Cohort 1 only**

Historical controls will be recruited at a ratio of 2 controls to every 1 rtPA + SOC arm patient, and will be matched according to the following characteristics:

1. Ventilation and oxygen type (IMV and non-invasive oxygen support)
2. Severity as determined by  $\text{PaO}_2/\text{FiO}_2$  ratio
3. Gender
4. Age (+/- 2 years, up to a maximum of 10 years)
5. Ethnicity

Matching will be done in the order that the characteristics are presented above.

Deceased patients can be considered for matching as controls. However, as a certain number of observations are required for developing a P/F ratio of the curve, patients who died within 48 hrs of admission are excluded.

Baseline data during admission will be used for matching.

An age range of +/- two years was used in the first instance, and this was widened until two eligible patients were identified that matched the treatment patient's ethnicity, up to a maximum of +/- 10 years.

Where more than two controls are identified, two controls will be drawn at random without replacement among all considered historical patients that match according to the characteristics above.

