## 10.6 Statistical analysis plan

All analyses will be descriptive in nature and should be considered as hypothesis generating rather than providing firm conclusions.

Analysis of cohorts 1 and 2 will be undertaken separately.

All study data will be listed and all relevant data will be tabulated and summarised separately by cohort and by group (rtPA treated, historical controls), separately for the patients receiving IMV, and for other patients with mild ARDS requiring non-invasive oxygen support at enrolment, and overall only where appropriate, as follows:

Planned recruitment for Cohort 1:

Group 1: Patients with ARDS receiving IMV at enrolment treated with rtPA (n=6)

Group 2: Patients with ARDS requiring non-invasive support at enrolment treated with rtPA (n=6)

Group 3: Patients with ARDS receiving IMV - historical controls (n=12)

Group 4: Patients with ARDS requiring non-invasive support - historical controls (n=12)

Planned recruitment for Cohort 2:

A total of 30 patients will be recruited, with a minimum of 10 from each ventilation type.

Group 5: Patients with ARDS receiving IMV at enrolment treated with rtPA

Group 6: Patients with ARDS requiring non-invasive support at enrolment treated with rtPA

Data will be presented using standard descriptive statistics. Continuous variables will be summarised using number of observations, mean, and standard deviation, median, inter-quartile range, minimum, and maximum values. Categorical values will be summarised using number of observations and percentages.

A statistical analysis plan will be written and finalised prior to database lock. This plan will give a detailed description of all summaries and results that will be presented. Cohort 1 data will be locked separately from the cohort 2 data and a separate SAP will be produced for the analysis of the cohort 2 data.

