### **10.6.2 Primary outcome analysis**

The PaO2/FiO2 ratio measured over time will be described for each group. The change from baseline in the PaO2/FiO2 ratio will be summarised at each post baseline timepoint. Plots will be used, where appropriate, to show the PaO2/FiO2 summarised for patients over time.

PaO2/FiO2 will be a calculated field on the trial database derived from the fields for PaO2 and FiO2. For cohort 2 data will be extracted once a day coinciding with the worst PF ratio. As PF ratio is the primary endpoint, in addition to the worst PF ratio, up to a maximum of 6 data points spread across 24 hrs that represents patients clinical status will be extracted. Details of further data derivation and analyses will be described in the SAP.

All patient data will be used, regardless of any intercurrent events that may have occurred after enrolment:

- Data from patients recruited into the rtPA + SOC group will be summarised whether or not patients have received all planned doses of the IMP.
- Any change in requirement for oxygenation and ventilation support will be summarised and described
- Changes in PaO2/FiO2 ratio over time will be described and interpreted taking into consideration that a patient's condition may have changed and led to their ventilation type changed post enrolment. If data allows, additional descriptions of the PaO2/FiO2 ratio over time may be performed in each subgroup of patients experiencing such changes (e.g. IMV to NIV, or vice versa).

The incidence and severity of bleeding events will be summarised in each group, and the change in fibrinogen levels will also be summarised at each post-baseline timepoint.

For cohort 1, subject to the final sample size and data quality, outcomes will also be compared between the SOC only group and intervention (rtPA + SOC) group using appropriate regression methods to make adjustment for baseline characteristics. Appropriate data transformations required for model assumptions will be considered if necessary.

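### The SAP's comparison with historical controls leaves out ventilation type and the matched sets, so its 95% interval is likely to be wider than necessary; the estimate itself is not biased by ventilation type.

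*SAP*

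**What the plan says.** SAP 6.3 compares end-of-treatment PaO2/FiO2 between rtPA patients and historical controls with a linear model. Its terms are treatment group, baseline PaO2/FiO2 and a "Normally distributed error term" for each patient. It then closes the list: "Owing to a limited sample size, models shall not adjust for other baseline characteristics". The group coefficient is reported with a confidence interval and p-value. SAP 6.1 sets the standard: "All statistical tests and confidence intervals will be 2-sided" and "Significance will be considered at the 5% level and confidence intervals will be at the 95% level".

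SAP section 4 and protocol 10.4.2 both describe two controls per treated patient, matched in order on ventilation type, PaO2/FiO2 severity, gender, age and ethnicity. SAP section 6 does not mention the matched sets.

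Protocol 10.6.2 foresees a comparison "using appropriate regression methods to make adjustment for baseline characteristics", without listing them. The protocol summary (section 1) speaks only of adjusting for baseline measurements. Protocol 10.6 has data tabulated and summarised "separately for the patients receiving IMV" and for those on non-invasive support, combining them only where appropriate. It defines Groups 1-4 of cohort 1 as treatment by ventilation type. SAP 6.2-6.4 say 'by group' without saying which grouping is meant.

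**The concern.** A matched design earns its precision only if the analysis uses the matching. Here the leading matching factor is excluded from the model, and the three members of each set are treated as unrelated. Any difference between ventilated and non-ventilated patients not carried by baseline PaO2/FiO2 stays in the residual, as does any similarity between members of a set. The standard error of the rtPA effect is then overstated.

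The stated reason, limited sample size, is weak for one binary term. There is some ground for thinking that ventilation type matters. Protocol section 1 describes the ventilated patients as having moderate to severe ARDS and the others as having mild ARDS. Protocol 2.5 reports, without a figure, that the oxygenation effect seemed smaller in ventilated patients. That second remark concerns the treatment effect and not prognosis, so it is only indirect support.

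At stake is precision in a very small comparison. Protocol 2.5 says the controls were recruited to evaluate efficacy so that a phase 3 sample size could be calculated. A residual variance inflated in this way could carry into that calculation.

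**Working it through.** **Inputs from the documents.** Planned: 12 treated + 2 × 12 controls = 36 (SAP section 1). Cohort 1 as closed: 9 treated (6 IMV, 3 non-invasive) + 2 × 9 = 18 controls, total 27 (protocol 4.1). Two-sided 95% intervals (SAP 6.1).

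**Assumed, because the documents do not give them.** Residual SD 70 mmHg; the stratum difference given baseline PaO2/FiO2; and the within-set correlation ρ remaining after baseline PaO2/FiO2.

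**1. The plan's own figure.** With independent errors and no ventilation effect, simulating the SAP model (4,000 runs) gives coverage of 94.9% with 9 sets and 94.7% with 12. Monte Carlo error is about 0.35 points, so the nominal 95% is reproduced under the SAP's own assumptions.

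**2. Price of the ventilation term.** Residual degrees of freedom go from 27 − 3 = 24 to 23, and the t multiplier from 2.064 to 2.069. At the planned size they go from 33 to 32 (2.035 to 2.037). This assumes every patient has an end-of-treatment value.

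**3. Ventilation type omitted, no set correlation.** If baseline PaO2/FiO2 is unrelated to ventilation type, the width ratio is approximately √[1 + d²p(1 − p)] × 2.064/2.069. Here d is the stratum difference divided by 70, and p = 6/9, so p(1 − p) = 2/9.

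| Stratum difference (mmHg) | d | Formula | Simulation, about |
|---|---|---|---|
| 20 | 0.286 | 1.007 | 0-1% wider |
| 40 | 0.571 | 1.033 | 2-3% wider |
| 60 | 0.857 | 1.076 | 5-7% wider |
| 100 | 1.429 | 1.203 | 14-20% wider |

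The formula sits at about the upper end. The more baseline PaO2/FiO2 itself separates the two ventilation types, the smaller the loss.

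**4. Matched sets ignored, no ventilation effect.** For m sets and no covariate, model SE / true SE = √[(1 − ρ/(3m − 2))/(1 − ρ)]. With m = 9 and ρ = 0.3 this is √(0.988/0.7) = 1.188.

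| ρ | Formula | Simulated SE ratio | Coverage of SAP interval |
|---|---|---|---|
| 0.1 | 1.052 | 1.04 | 96.2% |
| 0.3 | 1.188 | 1.17 | 97.8% |
| 0.5 | 1.400 | 1.35 | 99.0% |

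**5. Both together, and what repairs it.** With ρ = 0.3 and a ventilation effect of 1 residual SD (9 sets; widths in residual SDs):

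| Model | Coverage | Mean width |
|---|---|---|
| SAP | 98.6% | 1.81 |
| SAP + ventilation type | 97.6% | 1.62 |
| SAP + fixed set effects | 95.4% | 1.47 |

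The last interval is 1 − 1.47/1.81 = 19% narrower than the SAP's. In mmHg, a set SD of 35 within a total residual SD of 70 gives ρ = 35²/70² = 0.25. The SAP model then covers about 97-99%, a ventilation term alone still about 97%, and set terms about 95%.

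**6. Bias.** Every set shares one ventilation type, so it is balanced between groups. The mean simulated estimate was within about 0.01 SD of the true value of zero in each setting.

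**7. Cost if nothing is there (ρ = 0, no stratum difference).** Mean width goes from 1.671 to 1.676 with the ventilation term (0.3%), and to 1.762 with fixed set effects (1.762/1.671 = 1.054, about 5%). A random set intercept was not simulated.

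**The case against.** The strongest reply is that a two-term model is a defensible choice in a small pilot. The comparison is made only if numbers and data quality allow. The SAP labels all analyses exploratory, and the sample size has no statistical basis. For stratum differences up to 40 mmHg, or ρ near 0.1, the loss is small. All of this stands and limits the consequence. It does not supply a reason to exclude the leading matching factor, since the term costs almost nothing.

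The SAP also has escape routes. Section 2.1 permits further analyses, and 6.3 says that "other suitable approaches (e.g., robust or non-parametric methods) shall be explored if model assumptions are not satisfied". But the fallback is conditional and does not mention matching, and 2.1 leaves the planned model as it is.

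A reader might infer that the SAP breaches the protocol. The documents do not establish that. Protocol 10.6.2 names no covariate and leaves details to the SAP. The baseline PaO2/FiO2 term satisfies the protocol summary. The separation by ventilation type in 10.6 governs summaries and not regression covariates. The SAP was also written to protocol version 7.0, while the protocol supplied is version 10.0, whose history records changes to the group definitions in 10.6.

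A reader might also infer that the SAP has dropped reporting by ventilation type. Its 'by group' is ambiguous: it could mean the protocol's Groups 1-4 or only rtPA versus control. That calls for clarification and does not show a loss.

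**Conclusion.** The point holds as one of precision. Omitting ventilation type and the matched sets leaves the rtPA estimate unbiased by ventilation type. It makes the interval too wide and the p-value conservative whenever strata differ beyond baseline PaO2/FiO2 or set members resemble each other. A reader might fear false-positive findings; for positive within-set correlation the error runs the other way.

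The documents cannot fix the size. Under an assumed residual SD of 70 mmHg with 9 sets, the excess width ranges from negligible at 20 mmHg to 14-20% at 100. Coverage is about 97-99% with a set SD of 35. A ventilation term alone does not restore 95% coverage when sets are correlated, so the sets must enter the model as well. This is a worthwhile, inexpensive improvement to an exploratory comparison.

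**What to change.** In SAP 6.3, replace the sentence barring other covariates with a main comparison model containing:

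- treatment group;
- baseline PaO2/FiO2;
- ventilation type (IMV or non-invasive), taken at enrolment for treated patients and at the matching baseline for controls;
- a matched-set effect, either a random intercept or fixed set effects. Fixed effects absorb ventilation type, so the separate term then drops out.

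The choice between random and fixed should be stated before analysis, and this should be the main model, not only a sensitivity analysis. State in SAP 6.2-6.4 that 'by group' means treatment by ventilation type, as in Groups 1-4 of protocol 10.6.

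No new clinical data are needed, but the analysis data set must hold the link between each treated patient and the two controls. The statistical cost is one degree of freedom for the ventilation term. With fixed set effects it is intervals about 5% wider if neither sets nor strata matter.

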## 4 Trial design

### 4.1 Overall design

This is a phase II, open label, single centre, uncontrolled, repeated dose, pilot trial of nebulised rtPA in patients with COVID-19 ARDS.

The study will recruit patients requiring either IMV or non-invasive oxygen support. Eligible patients (or if patients lack capacity, their legal representative) will be provided with an information sheet and informed consent will be sought (see section 6.3). Eligibility will be assessed via routine clinical assessments, which may have been done prior to consent. The only exceptions are a pregnancy test (blood or urine), and possibly any assessments listed in section 7.1 that were not done as per routine care. These must be done following consent, and all screening assessments must have been done during the 24-hour period before dosing with rtPA.

The study will run two cohorts sequentially. In cohort 1, 9 consented patients received nebulised rtPA in addition to SOC. 6 patients were receiving IMV and 3 were receiving non invasive support with NIV or CPAP or high flow oxygen or standard oxygen therapy. As an observational arm, matched historical controls who received standard of care were also recruited at a ratio of 2 controls to every 1 treatment arm patient, resulting in 18 historical controls. Originally, the study aimed to recruit 12 patients with 6 on each ventilation type (IMV and non-invasive oxygen support). This would have resulted in 24 historical controls. After the first wave of COVID-19 cases decreased in August 2020 in the UK it became difficult to continue recruitment, so recruitment closed for cohort 1.

With a second surge underway in early 2021, cohort 2 will aim to recruit more patients during this period to provide more data on the safety of rtPA. Based on the analysis of cohort 1, fewer timepoints will be collected (see sections 7.1.2 and 7.5.2), which will allow for more rapid recruitment while at the same time not compromising safety monitoring. A more flexible dosing regimen for rtPA will be utilised which is described in section 7.3.2. 30 patients will be recruited in total, with an aim to recruit a minimum of 10 IMV patients and 10 patients on non-invasive oxygen support.

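### Primary safety counts carry no interval, and patients below the fibrinogen threshold are not tabulated, so the small groups' results would not show how little they exclude

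*SAP*

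**What the plan says.** Efficacy and safety are both primary in Protocol 10.1 and SAP 5.1. The safety endpoints are major bleeding (attributable to the drug, in the Protocol's wording), a fall in fibrinogen below a threshold, and serious adverse events causally related to treatment.

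SAP 6.3 plans them as follows:

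- Bleeding: "the incidence and severity (either major or minor) of bleeding events will be summarised with frequencies and percentages in each group".
- Fibrinogen: "Fibrinogen levels will also be summarised graphically using plots of the mean, by group, over time".
- Serious adverse events: "the number and nature of serious adverse events (SAEs) will be summarised".

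None of these has an interval. For the PaO2/FiO2 model, the same section wants the estimated group coefficient "and associated 95% confidence interval shall be reported, as well as a p-value pertaining to the hypothesis test of" no group difference. SAP 6.1 sets a convention for any interval that is used ("All statistical tests and confidence intervals will be 2-sided", and "confidence intervals will be at the 95% level") but does not say that safety proportions get one.

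Protocol 10.6 applies to both cohorts: "Categorical values will be summarised using number of observations and percentages". Protocol 10.6.2 adds only that bleeding will be summarised by group and that change in fibrinogen will be summarised at each timepoint. On purpose, Protocol 4.1 says that "cohort 2 will aim to recruit more patients during this period to provide more data on the safety of rtPA".

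**The concern.** A percentage from a group of 3 to 30 patients says little unless the reader also sees the range of true rates that it leaves open. Zeros are likely on two of the primary safety endpoints. Protocol 2.5 reports that no cohort 1 bleed was considered related to rtPA, and Protocol 2.7.3 reports that no cohort 1 patient had fibrinogen below 1.5 g/L. A bare zero can easily be read as evidence that the regimen does not cause the event.

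The figures also feed a decision. Under Protocol 12.2 the DMC is to use the safety and efficacy data to advise on moving to a randomised trial. Protocol 10.4.1 says that neither sample size rests on a statistical consideration, so no precision for safety is stated anywhere else.

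For fibrinogen the gap is wider. A plot of group means cannot show whether any one patient crossed the threshold that defines the endpoint.

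**Working it through.** The plan states no precision or sample-size figure for safety, so there is none to reproduce.

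**Inputs**

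- Cohort 1 treated: 9 patients, 6 on IMV and 3 on non-invasive support (Protocol 4.1).
- Cohort 2: 30 patients, at least 10 per ventilation type (Protocol 10.6).
- Preliminary cohort 1 events: no bleed considered related (Protocol 2.5); no patient below 1.5 g/L fibrinogen, and therefore none below 1.0 g/L (Protocol 2.7.3); 7 bleeds of any cause, one of them ISTH major (Protocol 2.7).
- Interval convention: two-sided 95%, so 0.025 in each tail (SAP 6.1).

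**Zero events.** The exact (Clopper-Pearson) upper limit for 0/n is the rate p at which (1 − p)^n = 0.025, so p = 1 − 0.025^(1/n).

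| Group | n | Upper limit for 0/n |
|---|---|---|
| Cohort 1, non-invasive | 3 | 1 − 0.025^(1/3) = 70.8% |
| Cohort 1, IMV | 6 | 1 − 0.025^(1/6) = 45.9% |
| Cohort 1, all treated | 9 | 1 − 0.025^(1/9) = 33.6% |
| Cohort 2, minimum per ventilation type | 10 | 1 − 0.025^(1/10) = 30.8% |
| Cohort 2, all | 30 | 1 − 0.025^(1/30) = 11.6% |

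The full 12 patients planned for cohort 1 would have given 26.5%. The choice of method does not change the message. For n = 9, 10 and 30, a one-sided 95% exact limit gives 28.3%, 25.9% and 9.5%, and the Wilson limit gives 29.9%, 27.7% and 11.3%.

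**One event.** For one patient of 9 with an ISTH major bleed of any cause, the exact limits are the 0.025 quantile of Beta(1, 9) and the 0.975 quantile of Beta(2, 8), which are 0.3% and 48.2%.

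**Chance of seeing no event.** For a true rate p this is (1 − p)^n. Protocol 2.6 says that bleeding frequencies by this route are unknown, so the rates it quotes for other uses of rtPA serve only as illustrations.

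| Assumed rate and its source in Protocol 2.6 | None in 30 |
|---|---|
| 1% (intracranial haemorrhage in myocardial infarction is quoted as below this) | 0.99^30 = 74% |
| 1.7% (major bleeding, pharmacomechanical thrombolysis) | 0.983^30 = 60% |
| 2% (other major haemorrhage, stroke) | 0.98^30 = 55% |
| 6% (symptomatic intracranial haemorrhage, stroke) | 0.94^30 = 16% |

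In 9 patients the last two become 0.98^9 = 83% and 0.94^9 = 57%.

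**The case against.** Three stronger readings are tempting, and the documents do not support them.

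- A reader might infer that the cohort 1 bleeding table will show 0%. It will not, on the preliminary data. The bleeding summary in SAP 6.3 is not limited to related events, and there were 7 bleeds, one of them ISTH major. Zero of 9 fits only related bleeds and low fibrinogen.
- A reader might infer that cohort 2 will also be reported without intervals. SAP version 1.0 was written to protocol version 7.0, before cohort 2 was added. Protocol 10.6 promises a separate cohort 2 SAP, which is not among the documents and may supply intervals. For cohort 2 the evidence is one general sentence on categorical data.
- A reader might take 2% and 6% as the rates to expect here. They come from intravenous use in acute stroke, which Protocol 2.6 describes as having the most bleeding events. The same section also quotes under 1% and 1.7% in other settings.

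The plan has real safeguards as well. Every analysis is labelled hypothesis generating, numbers of observations accompany percentages, and all data are to be listed. The DMC receives weekly bleeding and fibrinogen reports in cohort 1 and meets after every 10 patients in cohort 2, and any stopping event triggers an ad hoc review. Safety monitoring therefore does not hang on one percentage.

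These points lower the severity. They do not remove the gap: a caveat and a visible denominator do not say which rates the data exclude, and the efficacy coefficient gets an interval under the same caveat.

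**Conclusion.** The point holds as a minor one. SAP 6.3 gives bleeding without an interval and never plans the fibrinogen threshold endpoint as a count of patients. In cohort 1, zero related major bleeds or zero patients with low fibrinogen would still be compatible with rates up to about a third overall, and with far more in the ventilation groups that Protocol 10.6 summarises separately. The any-cause major bleeding rate would be known only to within 0.3% to 48.2%.

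This rests on the preliminary cohort 1 counts, which the Protocol says are not final, on the single ISTH major bleed counting as one patient, and on the two-sided 95% convention of SAP 6.1. The cohort 2 limits apply only if no events occur, and the gap there exists only if the cohort 2 SAP does not already add intervals. The documents do not show that any safety conclusion has been or will be wrongly drawn.

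**What to change.** First reconcile the fibrinogen endpoint: Protocol 10.1.2 gives a threshold of 1.0 g/L and SAP 5.1 gives 1.5 g/L. Which is intended is for the sponsor to settle.

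Then state in SAP 6.3 and Protocol 10.6.2, and carry into the cohort 2 SAP, that the safety table reports the number of patients with at least one:

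- related major bleed;
- major bleed of any cause;
- bleed of any kind;
- fibrinogen value below the reconciled threshold in the endpoint window.

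Each is given as n/N with the exact (Clopper-Pearson) two-sided 95% interval, by ventilation group and overall within cohort. Counting patients also settles the denominator, since Protocol 2.7 reports cohort 1 bleeds by event. The fibrinogen plots can stay alongside.

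The cost is one column in the safety table, and a safety result that looks less favourable. No new data or design change is needed.
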